This is a single site, feasibility, randomized, dose-ranging clinical trial of remote ischemic preconditioning. During periods of active treatment, induced twice a day by using the autoRICTM device around both upper body extremities which would deliver four remote ischemic conditioning cycles of five minute intervals followed by five-minutes of normal blood flow. The RPreC intervention will be add-on therapy to guideline-based best standard medical prevention therapy. The study will have a randomized phase and a follow-up phase. 60 enrolled patients will be randomized 1:1:1 to 1 year of best standard medical care alone, best standard medical plus active once-daily RPreC, or best standard therapy plus active twice-daily RPreC. Following the 1 year randomized phase, the medical control group will cross over to once (10 patients) and twice (10 patients) daily RPreC for 1 additional year (staggered start design, allowing for collection of additional feasibility and safety data and control group adherence to follow-up). Primary outcome measures will be obtained at the end of the first randomized year.

C.2. Technology

Remote Ischemic Preconditioning Device: The autoRICTM device is a new, portable, automated conditioning device, designed and developed by CellAegis Devices Inc., Canada. The device consists of a Control Unit, Charging Cradle, a Power Adaptor, a Wall Mount for the charging cradle (with wall plug and screws) and Applicator Cuffs. The control unit is a stand-alone reusable controller that controls the inflation and deflation cycles of the Applicator Cuff. The Control Unit clicks into the disposable Applicator Cuff when it is ready for use. The Applicator Cuff is a single-used, disposable cuff that is fastened using Velcro into which a 'one button' battery-driven actuator system inserts. This provides for a mobile 'point-of-care' delivery of RIC that will not impose on other care delivery, and requires no special expertise for its use. The active device is programmed to inflate the cuff to 200 mmHg for five (5) minutes (ischemia) then be deflated for five (5) minutes (reperfusion) completing one cycle of ischemia-reperfusion; the RIC therapy cycle consists of a total of four (4) cycles of ischemia-reperfusion, which the autoRIC Device is programmed to automatically deliver.

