All participating investigators and site personnel that will be performing the autoRIC procedure will be trained in the use of the study device prior to participating in the study. Device training will be conducted by the Principal Investigator. Training will be done according to the autoRIC User Manual and will include instructions on charging the device prior to the first use, recharging the device after each procedure, verifying the device is charged prior to each procedure, recognizing and addressing the different Warning/Error indications (e.g., battery light flashing blue, indicating that the battery is low but can still perform at least one procedure, battery light steady red, indicating battery low error – not enough battery power to run a complete procedure, etc.) and specific instructions for returning the device to the sponsor in the event of an error notification that cannot be addressed by the site personnel, or a failure of the device to charge after three hours.

All device training will be documented in a training log that will be maintained in the site regulatory binder.

C.3. Subjects

60 subjects will be identified prior to discharge from the inpatient Stroke Service, which manages over 350 patients yearly, and from the inpatient rehabilitation unit that cares for 100 patients yearly with disabling stroke. They will also be identified in our outpatient stroke clinic that manages over 500 patients yearly. Based upon a review of the past 5 years of stroke patients evaluated, we anticipate that at least 20% are likely to be eligible. Potential participants will be approached by an investigator and given the informed consent from to review. Enrolled subjects will be randomized 2:1 to active treatment (40 patients) and control (20 patients).

C.3.1.Entry Criteria

To enter the study screening phase, patients must meet all of the following inclusion and exclusion criteria:

Inclusion Criteria

I. Clinical

- 1. Clinical lacunar stroke syndrome within the past 6 months (from among the following 12 syndromes as per SPS3 criteria: pure motor hemiparesis (PMH), pure sensory stroke, sensorimotor stroke, ataxic hemiparesis, dysarthria-clumsy hand syndrome, hemiballism, PMH with facial sparing, PMH with horizontal gaze palsy, PMH with contralateral III palsy, PMH with contralateral VI palsy, cerebellar ataxia with contralateral III palsy, pure dysarthria)
- 2. Absence of signs or symptoms of cortical dysfunction

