Following the randomization assignment, all patients will have follow-up visits at 1, 3, 6, 9, and 12 months. Feasibility, safety, and efficacy assessments will be performed at each of these visits, with the 12 month measures, at the conclusion of the randomized phase, constituting the primary outcome timepoint. In addition, the 20 control patients will have follow-up visits at 18 and 24 months, during the period of their delayed start therapy. The cognitive assessment battery will be performed at the first qualifying visit to familiarize participants with the system before the baseline assessment at randomization and additionally at 1 month to assess whether any cognitive changes accompanied the initial RPreC effect. If participants ceased study treatment during the study, they will be encouraged to continue attending follow-up visits; all withdrawn participants will be invited to attend the closeout visit to reduce loss to follow-up.

C.10. Treatment Evaluation

C.10.1. Baseline Evaluation

At study entry, enrolling investigator to record:

- Demographic data (age, sex, vascular risk factors)
- Heart rate
- Blood pressure
- Visual inspection of skin in arms, motor and sensory examinations of the hand
- NIH Stroke Scale (NIHSS)
- Modified Rankin Scale (mRS)
- Barthel Index (BI)
- EQ-5D (health-related quality of life)
- Questionaire to verify stroke free status
- Neurocognitive battery
- MR imaging will be reviewed
- Eligibility for enrollment
- Review informed consent with patient

C. 10.2. Day 30 Evaluation

- Interval Events Form
- Concomitant therapies form
- Heart rate
- Blood pressure
- Visual inspection of skin in arms, motor and sensory examinations of the hand
- NIH Stroke Scale (NIHSS)
- Modified Rankin Scale (mRS)
- Barthel Index (BI)
- EQ-5D (health-related quality of life)
- Questionaire to verify stroke free status

- Patient-reported Comfort Rating Scale a 5 point Likert scale reflecting patient report of subjective experience of RPreC (very comfortable, comfortable, average, uncomfortable, very uncomfortable) (Wang X, Maurin M. Discomfort/Comfort assessment using an ordered category scale.)
- Number of completed 5-minute cycles of RIPC
- Neurocognitive battery

C. 10.3. Month 3, 6, and 9 Evaluations

- Interval Events Form
- Concomitant therapies form
- Heart rate
- Blood pressure
- Visual inspection of skin in arms, motor and sensory examinations of the hand
- NIH Stroke Scale (NIHSS)
- Modified Rankin Scale (mRS)
- Barthel Index (BI)

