To ensure that appropriate ethical consideration is given to the welfare of the patients enrolled in the study, a Data and Safety Monitoring Board (DSMB) will oversee the trial. The DSMB will review the incidences and circumstances of adverse events that occur during the course of the trial. Formal interim analysis will occur at the half way -point, after enrolled patients have completed 50% of patient months of follow up. If the incidence of recurrent stroke or all serious adverse events is higher in the combined device arm than the control arm the study will be placed on hold. The DSMB will conduct a detailed analysis of the safety data. The DSMB may recommend making changes it deems necessary in the interests of the safety or well-being of the study subjects, or suspending or stopping the study. Final determination of a formal stopping rule will be the prerogative of the appointed DSMB.

The members of the DSMB are:

[name], Stroke Neurologist, University of Southern California [name], Stroke Neurologist, Rancho Los Amigos National Rehabilitation Center

C. 14.2. Statistical Design and Analysis Plan

The demographic and baseline clinical characteristics of the study population will be delineated with standard descriptive statistics. Categorical variables describing the clinical history, examination findings, and initial treatment will be summarized by frequencies. Continuous variables such as vital signs, laboratory results, and time variables that follow normal distribution

will be characterized by means, standard deviations, and 95% confidence intervals (CI). Ordinal and non-normally distributed variables (such as the NIHSS) will be characterized by medians and interquartile ranges. RIPC and control patients will be compared to delineate covariate balance. Wilcoxon Rank-Sum tests will be used for continuous or ordinal variables; Fisher's exact tests and chi-square tests will be used for grouped or nominal categorical variables. Comparisons of changes across time (i.e. base to one year) within and between groups will be made using repeated measure analysis variance methods or the non-parametric analog.

C. 14.3. Selection and Analysis of Endpoints

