Additional efficacy endpoints explored will include accelerometer assessment of gait quantity and quality in real-world activity; z scores on individual tests and summed performance on the cognitive battery, and incident ischemic stroke, transient ischemic attack, hemorrhagic stroke, myocardial infarction, and cardiovascular death. To protect against bias in ascertainment of the recurrent stroke secondary endpoint, analysis to include a) adjudication of potential endpoint stroke events by 2 independent blinded neurologists (preventing rater bias), and b) administration of the Questionnaire to Verify Stroke Free Status at each follow-up visit, to trigger endpoint evaluations (preventing ascertainment bias).

C.14.4. Sample Size Calculations

Subject size is typical sample size for a feasibility study with a device. We are looking at adherence in order to plan a larger phase II/III successor trial.

Sample Size Justification

The primary feasibility and study endpoint is RPreC adherence at 12 months. As we do not expect clinically important differences in adherence among the three groups, it may be possible to combine two or all three groups. In this study, we also wish to test the null hypothesis that the true adherence is at least 75%. The table below gives the lower 90% or 95% confidence bound for 90%, 95% or 100% observed adherence as a function of sample size and the corresponding statistical power for testing the null hypothesis that the true population adherence is 75% versus the one sided alternative of greater than 75%. The current study is not necessarily sufficiently powered for any of the safety or efficacy outcomes. Therefore this is a pilot study in terms of safety and efficacy.

Lower 90% or 95% one sided confidence bound for true adherence

| | adherence=90% | | adherence=95% | | adherence=100% | |
|----|---------------|------------|---------------|------------|----------------|----------------|
| | 90% | 95% | 90% | 95% | | |
| Ν | confidence | confidence | confidence | confidence | 90% confidence | 95% confidence |
| 20 | 75.5% | 71.8% | 81.9% | 78.5% | 89.1% | 86.1% |
| 40 | 81.0% | 78.5% | 87.2% | 85.1% | 94.4% | 92.8% |
| 60 | 83.1% | 81.2% | 89.2% | 87.6% | 96.2% | 95.1% |

Power for one sided test against null hypothesis of 75% vs > 75%

| | adherence=90% | | adherence=95% | | adherence=100% | |
|----|---------------|------------|---------------|------------|----------------|------------|

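### C.14.2 tests change within groups as well as between them and does not reserve the efficacy conclusion for the between-group contrast

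*Combined protocol and SAP*

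**What the plan says.** Section C.14.2 (Statistical Design and Analysis Plan) states: "Comparisons of changes across time (i.e. base to one year) within and between groups will be made", by "repeated measure analysis variance methods or the non-parametric analog". It does not name the group-by-time contrast, does not call the within-group results descriptive, and does not say which result would support an efficacy statement. It also does not list the outcomes to which the sentence applies.

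The groups are described in two ways. C.3 says "Enrolled subjects will be randomized 2:1 to active treatment (40 patients) and control (20 patients"), and section A also gives 2:1. C.1 says "60 enrolled patients will be randomized 1:1:1 to 1 year of best standard medical care alone" or one of two device schedules, which makes three arms of 20, and C.6 also describes three arms. C.14.2 uses two groups for the baseline comparison ("RIPC and control patients will be compared to delineate covariate balance") but does not say whether the device arms are pooled for the analysis of change.

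Three further sections matter here:
- **C.14.3** defines the lead MRI endpoint as the proportion of patients whose lesion volume rises above a threshold. Gait, cognitive scores and clinical events are additional, exploratory efficacy endpoints.
- **C.10** has disability, function and quality-of-life scales recorded at baseline and at each visit.
- **C.14.4** describes the study as a pilot for safety and efficacy.

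**The concern.** A within-group test asks whether patients changed. It does not ask whether the device changed them. The documents give reasons to expect some improvement in both arms. Patients enter within 6 months of a lacunar stroke. Some are found early ("60 subjects will be identified prior to discharge from the inpatient Stroke Service"), although C.3 also recruits from a rehabilitation unit and an outpatient clinic. The cognitive battery is repeated at baseline and at Months 1, 3, 6, 9 and 12.

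If both arms improve equally, the larger group is more likely to reach significance. A result that is significant in the device group and not in controls could then be reported as a signal of efficacy when the arms did not differ. C.14.4 concedes that power for efficacy may be insufficient, so a non-significant between-group test beside a significant device-group test is a plausible outcome. The plan should say in advance how to read it.

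**Working it through.** **The plan's own figures.** The documents give no power or error rate for the analysis of change. The only power table is in C.14.4 ("Power for one sided test against null hypothesis of 75% vs > 75"%), for adherence. An exact binomial test reproduces it. With N=40 and one-sided alpha 0.05, the test needs 35 or more adherent patients and has size 0.043; its power at 90% adherence is 0.794, as stated. All 12 entries for 90% and 95% adherence agree to within 0.001, and the confidence bounds agree to within 0.1 point. That table does not bear on the question here.

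**Inputs.**
- Group sizes: 40 and 20 (C.3), or 20/20/20 (C.1).
- Level: two-sided 0.05. This is an assumption, because C.14.2 gives none.
- Shared change d, in units of the SD of change and equal in both arms: an assumption, varied from 0 to 1.0.
- Device effect: none.
- Test: one-sample t-test of change in each group, with normal data. The rank-based alternative was not calculated.

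**Formula.** Let p(n) be the power of the one-sample t-test with non-centrality d√n. The arms are independent, so

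- device only = p(40) × [1 − p(20)]
- control only = p(20) × [1 − p(40)]

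At d = 0.4 the non-centralities are 0.4√40 = 2.53 and 0.4√20 = 1.79, giving p(40) = 0.694 and p(20) = 0.397. Device only = 0.694 × 0.603 = 0.418. Control only = 0.397 × 0.306 = 0.121.

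| Shared change d | Device significant (n=40) | Control significant (n=20) | Device only | Control only | One group only, 30 v 30 |
|---|---|---|---|---|---|
| 0 | 0.050 | 0.050 | 0.048 | 0.048 | 0.047 |
| 0.2 | 0.235 | 0.136 | 0.203 | 0.104 | 0.151 |
| 0.3 | 0.457 | 0.247 | 0.344 | 0.134 | 0.229 |
| 0.4 | 0.694 | 0.397 | 0.418 | 0.121 | 0.246 |
| 0.5 | 0.869 | 0.565 | 0.379 | 0.074 | 0.186 |
| 0.6 | 0.959 | 0.721 | 0.268 | 0.030 | 0.099 |
| 0.8 | 0.999 | 0.924 | 0.076 | 0.001 | 0.011 |
| 1.0 | 1.000 | 0.989 | 0.011 | 0.000 | 0.000 |

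The last column is the chance that one named group is significant and the other is not.

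**Maxima over d.**
- 40 v 20, device only: 0.42 at d about 0.415 (0.726 × 0.578). The normal approximation gives 0.41.
- 40 v 20, control only: 0.136 at d about 0.325.
- Two equal groups: p(1 − p), which cannot exceed 0.25.
- Three arms of 20, at least one device arm but not control: [1 − (1 − p)²](1 − p), maximum 0.385.
- Three arms of 20, one named device arm but not control: maximum 0.25. Both device arms but not control: p²(1 − p), maximum 0.148.

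**The between-group test.** In 100,000 simulated trials at each of d = 0, 0.2, 0.4 and 0.6 (40 v 20), a t-test of the difference in change was significant in 4.8% to 5.0%. The device-only pattern together with a significant between-group test occurred in 1.1% to 2.4%.

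**Direction.** The device-only pattern flatters the device only when the shared change is an improvement. Where both arms worsen (mean lesion volume, atrophy), it would falsely suggest harm. The flattering pattern is then control only, which peaks at about 14%.

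**The case against.** The strongest reply is that the between-group comparison is already planned in the same sentence, and that no section says efficacy will be read by setting one group's p-value against the other's. That is correct. A reader might infer that the plan lacks a controlled comparison, or that it builds in a 4-in-10 false-positive rate. The documents support neither reading. What they lack is a rule saying which result counts.

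Several narrower objections also stand.
- **Scope.** A reader might apply the 42% to every outcome. The lead MRI endpoint is a proportion, and stroke, TIA, infarction and cardiovascular death are incident events, so none has a within-group mean change to test. Outcomes that worsen run the other way.
- **Cause.** A reader might blame the 2:1 allocation alone. Equal groups still reach 25%, so unequal size enlarges the problem but does not create it. Under the three-arm text, 40 against 20 also requires pooling.
- **Size of the shared change.** No document supports 0.3 to 0.5 SD in particular, and those values lie near the peak.
- **Practice effects.** C.9 says: "The cognitive assessment battery will be performed at the first qualifying visit to familiarize participants with the system before the baseline assessment". A session before baseline is a safeguard that should reduce later practice gain, although it does not guarantee there is none.
- **Stakes.** C.14.4 plans the successor trial on adherence, and C.11 notes that the primary endpoint makes no use of the control group.

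These points limit the size and importance of the concern. They do not remove it, because the within-group test remains in the plan without a stated role.

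**Conclusion.** The concern holds in a limited form, and its severity is minor. It applies to exploratory continuous or ordinal outcomes that improve in both arms: cognitive tests, and the function and quality-of-life scales if they are analysed for change. For these, with no device effect, a result significant in the device group only would occur in about 5% of trials with no shared change, 20% at 0.2 SD, at most about 42% near 0.4 SD, and 8% at 0.8 SD. The between-group test holds its 5% throughout.

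These figures rest on a two-sided 0.05 level, pooled device arms, t-tests on normal data, and an assumed shared change that the documents do not give. If the arms are kept separate, the maximum is about 38% for at least one device arm and 25% for a named one. The feasibility conclusion and the lead MRI endpoint are untouched.

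**What to change.** Amend the C.14.2 sentence to say that:
- efficacy is judged only by the between-group difference in change (the group-by-time contrast, with 12 months as the primary timepoint), reported with its 95% CI;
- change within a group is summarised by mean or median with spread, without p-values.

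The other planned visits, including cognition at Month 1, can stay in the between-group repeated-measures analysis. State the significance level and whether the device arms are pooled for this analysis. Separately, reconcile the 2:1 text (sections A and C.3) with the 1:1:1 text (C.1), since the groups being compared depend on it.

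The cost is wording only: no extra data, visits or patients, and fewer tests to run.

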This aim will be accomplished by assessing safety outcomes in patients undergoing remote ischemic preconditioning treatment. The primary safety endpoint will be all serious adverse events. Secondary safety endpoints will include deep and superficial vein thrombosis and all-cause mortality. Ascertainment that RPreC poses no major excess risk to patients will allow for subsequent efficacy testing in a larger clinical trial.

A.3. Specific Aim 3: Signals of Efficacy

To employ imaging biomarkers to demonstrate biologic efficacy of remote ischemic preconditioning as a sustained therapy for prevention of ischemic brain injury from cerebral small vessel disease, and to employ cognitive, ambulation, and clinical stroke event outcome measures to explore potential clinical efficacy.

This aim will be accomplished by measuring volumetric progression of white matter ischemic injury on magnetic resonance imaging (biomarker efficacy) and cognitive battery performance,

ecologic ambulation assessment, and recurrent stroke events (clinical efficacy). MRIs will be performed at baseline and at 1 year (end of randomized phase) and several markers of injury progression assessed, including FLAIR hyperintensity volumetric burden (primary biomarker efficacy outcome), diffusion tensor imaging volumetric burden, and cerebral atrophy. Wireless sensors will be used to assess gait quantity and quality in real-world activity at baseline and 1 year. A cognitive battery sensitive to executive, attentional, and memory function, reflecting subcortical-frontal system integrity, will assess progression of vascular cognitive impairment. Lastly, clinical events during the year of randomized therapy will be compared across treatment arms, including ischemic stroke, transient ischemic attack, hemorrhagic stroke, myocardial infarction, and cardiovascular death.

C. Trial Design

C.1. Study Overview

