Feasibility: Because the primary aim of this trial is assessing feasibility and tolerability, the primary endpoints are descriptive statistics describing the implementation of the RPreC procedure, including behavioral adherence to treatment, physiologic attainment of limb ischemia, and patient self-reported comfort-discomfort during treatment. The simplicity of these endpoints reduces the likelihood of problems in the analysis and interpretation of these endpoints. The procedure will be considered adequately feasible if adherence and physiologic targets are attained in 75% or more of cases. At this early stage of development, observations and lessons from individual cases may warrant procedural protocol changes to optimize the intervention. Such flexible, developmental iterations of the intervention will be closely discussed with, and supervised by, the study DSMB.

Safety: The lead safety endpoint will be all serious adverse events. Secondary safety endpoints will be deep and superficial vein thrombosis and all cause mortality.

Efficacy: The lead efficacy endpoint will be volumetric progression of white matter ischemic injury on magnetic resonance imaging (biomarker efficacy). The primary MRI endpoint will be the proportion of patients with increase in total white matter hyperintensity volume (as percent of total brain volume) above 1.0%. (This value represents the threshold for the upper quintile of progression in the SCOPE trial. Proportion of patients with progression in the upper quintile was the most sensitive MR endpoint analyzed in the SCOPE substudy.) Additional MRI endpoints analyzed will include mean progression total white matter hyperintensity, mean and quintile progression in deep white matter hyperintensity, progression in total brain atrophy, and progression in DTI anisotropy. The MR imaging measures of white matter injury progression, ascertained by automated analysis and blinded readers, are not subject to bias.

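### Baseline-to-Year-1 repeated-measures ANOVA leaves out patients without a Year 1 value, along with their interim cognitive visits, and can favour an ineffective device if declining device patients are lost more often than declining controls

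*Combined protocol and SAP*

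**What the plan says.** C.14.2 defines the comparison as "Comparisons of changes across time (i.e. base to one year") and says that comparisons "within and between groups will be made using repeated measure analysis variance methods" or a non-parametric analog. It names no analysis set, no rule for missing values and no covariates. No other section supplies a mixed model, imputation, an expected dropout rate or a sensitivity analysis.

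C.9 states that "all patients will have follow-up visits at 1, 3, 6, 9, and 12 months". The neurocognitive battery is listed at baseline (C.10.1), day 30 (C.10.2), months 3, 6 and 9 (C.10.3) and Year 1 (C.10.4). MRI is different: under A.3, "MRIs will be performed at baseline and at 1 year (end of randomized phase").

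On retention, C.9 urges patients who stop treatment to keep attending, and "all withdrawn participants will be invited to attend the closeout visit to reduce loss to follow-up". C.6 gives controls device therapy in Year 2, partly to keep them in the study during Year 1. Device patients exit at the end of Year 1.

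On allocation, C.3 says: "Enrolled subjects will be randomized 2:1 to active treatment (40 patients) and control (20 patients"). C.1 instead gives three equal arms, which also pool to 40 device and 20 control patients.

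**The concern.** Repeated-measures ANOVA on two time points needs both values. So do the usual non-parametric analogs: a rank test on change needs both, and a Friedman-type test needs complete blocks. A patient who leaves after month 9 may have four follow-up cognitive assessments (months 1, 3, 6 and 9), and none of them counts.

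Loss could plausibly differ between the arms. In Year 1 only device patients have a treatment to stop, and section A concedes that the treatment has nuisance aspects and that long-term compliance is unknown. Only controls are offered something in Year 2. If device patients who leave are also those who are declining, the remaining device patients are a favourable selection compared with a nearly complete control arm.

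C.11 calls the outcomes robust against bias, but the safeguards it lists address rater and ascertainment bias, not attrition. At stake are the cognitive signals of efficacy in Aim 3, in a trial meant to inform a larger successor (C.14.4).

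**Working it through.** **The plan's own figures.** The only power table (C.14.4) concerns adherence. It reproduces with an exact binomial test: for N = 40 and true adherence 90%, rejecting at 34 or more gives 0.900 (stated 0.901, alpha 0.10), and at 35 or more gives 0.794 (stated 0.794, alpha 0.05). No SD, dropout rate or power is given for the change outcomes, so everything below rests on stated assumptions.

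**Source of the bias.** With two time points, the group-by-time test equals a t-test on change. Let an arm lose a fraction p of its patients, and let the mean change of those lost be g worse than the arm's mean. The completers' mean is then too favourable by g × p/(1−p). With no true effect:

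bias towards device = g_D × p_D/(1−p_D) − g_C × p_C/(1−p_C)

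This is zero if loss is unrelated to change (g = 0 in both arms) or if loss is the same in both arms.

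**Worked case.** Assumed: baseline SD 1 (including visit noise), visit noise SD 0.45, slope SD 0.6 per year. The SD of 12-month change is √(0.6² + 2 × 0.45²) = √0.765 = 0.87. Dropout is logistic, 2 logits per SD of the change already seen at 6 months, and costs months 9 and 12. Integrating that dropout curve over a normal distribution gives g of about 0.80 at 5% loss, 0.70 at 10%, 0.57 at 20% and 0.476 at 30%. With control loss 5%, the control term is 0.0526 × 0.80 = 0.042, so:
- device loss 10%: 0.111 × 0.70 − 0.042 = 0.036
- device loss 20%: 0.250 × 0.57 − 0.042 = 0.100
- device loss 30%: 0.429 × 0.476 − 0.042 = 0.162

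**Simulation of the same model.** 40 v 20 patients, visits at 0, 1, 3, 6, 9 and 12 months, no device effect, 1,500 trials per scenario, Monte Carlo SE 0.006 to 0.007. Bias towards the device in SD at device loss 10% / 20% / 30%, control loss 5%:

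| Loss driven by | Two-point ANOVA | Baseline-adjusted completers | Likelihood model, all visits |
|---|---|---|---|
| Decline seen at 6 months | 0.03 / 0.10 / 0.16 | 0.03 / 0.09 / 0.14 | 0.00 / 0.00 / 0.00 |
| Unseen 12-month decline | 0.05 / 0.16 / 0.26 | 0.05 / 0.16 / 0.25 | 0.03 / 0.10 / 0.16 |

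The rate of false significant benefit from the ANOVA (nominal 2.5%) was 3.7 to 8.5% in the first row and 3.9 to 21.0% in the second.

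**When there is no such bias.** Loss unrelated to outcome gave at most 0.015 SD. Loss driven by baseline only gave −0.03 to −0.05 SD for the ANOVA (against the device) when device loss was higher. Loss of decliners equal at 20% in both arms gave −0.004 (seen) and 0.013 (unseen).

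**Two further null simulations, 40 v 20.**
- Baseline-to-12-month correlation 0.50 or 0.66, 3% missed visits, and a dropout risk per visit 10 or 25 points higher for device patients with a fall over 0.5 SD. Loss was 17 to 31% v 7%. Two-point bias was 0.061 to 0.187 SD, baseline-adjusted completers 0.042 to 0.111, and the all-visits model at most 0.005 with the covariance taken as known. False benefit from the two-point analysis was 4 to 9%.
- Unstructured covariance estimated from the 60 patients, loss of 15 to 26% v 7%, driven by observed decline. Two-point bias was 0.04 to 0.15, baseline-adjusted completers 0.03 to 0.13, and the all-visits model −0.02 to 0.00, with no loss of precision.

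For loss that follows observed decline, the two-point bias therefore spans about 0.03 to 0.19 SD.

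**The case against.** **The exclusion is inferred.** C.14.2 names a family of methods and states no exclusion rule. That is fair. Restriction to patients with both values follows from the usual form of the method, and a plan silent on the matter still needs a rule.

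**A reader might infer that any missed visit removes a patient.** At 5% missed per visit that would leave 0.95⁵ = 77%, or 46 of 60. The text does not support this: it limits the comparison to baseline and one year, so two values are needed, not six.

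**Selective loss is not documented.** This stands. No section gives a dropout rate or links withdrawal to decline. The supervised tolerance test before randomisation (C.8) and exclusion criterion 28 should reduce device-driven loss. Nor does the feasibility rule, "considered adequately feasible if adherence and physiologic targets are attained in 75% or more of cases", license an expectation of 25% missing data: stopping treatment is not leaving the study, and C.9 separates the two.

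**The closeout invitation could recover Year 1 values.** It could. In a similar null simulation, attendance by half of withdrawn patients cut the two-point bias from 0.04–0.18 to 0.02–0.07 SD and false benefit from 4–8% to 3–4%. At 75% attendance the bias was 0.01–0.04 SD. Attendance is unknown.

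**The mixed model is not a full cure.** Its near-zero bias depends on loss following observed values. Under unseen decline it kept 0.10 to 0.16 SD at 20 to 30% device loss. An unstructured covariance for six visits has 6 × 7/2 = 21 parameters, although estimating it from 60 patients worked in the simulation above.

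**The affected outcomes are exploratory.** C.14.4 calls the trial a pilot for efficacy, the primary adherence endpoint does not use this analysis, and the lead MRI endpoint is a proportion (C.14.3). This limits the consequence but does not remove the reason to use data already scheduled.

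**Conclusion.** The point holds in a limited form. The named method, as usually applied, sets aside the interim cognitive data of patients without a Year 1 value, and nothing in the plan replaces it. If declining device patients are lost more often than declining controls, an ineffective device gains roughly 0.03 to 0.19 SD when loss follows decline already seen at visits, and up to 0.26 SD at 30% device loss that follows unseen decline. Adjusting for baseline among completers would leave most of this.

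A reader might conclude that the plan will make a useless device look beneficial. The documents do not support that. The mechanism needs loss that is both unequal and related to decline, which is plausible here but assumed. Even then, with loss following observed decline, more than 90% of null trials showed no false significant benefit. The likelier harm is a shifted estimate carried into planning of the successor trial.

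The primary adherence endpoint is unaffected. Selective loss could also distort the MRI endpoints, but with scans only at baseline and one year the change proposed here cannot repair them. Gait is uncertain: A.3 has it at baseline and one year, C.10.3 and C.10.4 list it at months 3, 6, 9 and 12, and the baseline list in C.10.1 omits it. Cognition is the firm case.

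**What to change.** In C.14.2, for outcomes with several follow-up visits (the cognitive battery, and gait once A.3 and C.10 are reconciled), replace repeated-measures ANOVA with a likelihood-based mixed model for repeated measures:

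- include every observed visit of every randomised patient, baseline included;
- fit arm, visit and arm-by-visit terms;
- use an unstructured covariance, falling back to random intercept and slope if it does not converge;
- report the month-12 arm contrast.

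Report by arm the number with a Year 1 value and the reasons for loss. Add one simple not-at-random sensitivity analysis, for example worsening the unobserved month-12 values of lost device patients by a range of fixed amounts, because the model only partly corrects loss that follows unseen decline.

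The cost is SAP wording, standard software and a short record of reasons for loss. No extra patients or visits are needed. The model assumes that loss depends on observed values, which is weaker than what the completer analysis assumes.
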